7.1.8 Proportion of Subjects Achieving Pre-defined Characteristic

Unless otherwise specified, the proportion of subjects *with a pre-defined characteristic* at Week *t* will be analyzed using logistic regression with adjustment for baseline HbA1c value and/or the stratification factor. Subjects in the randomized treatment group who do not demonstrate achieving therapeutic glyceemic response at a specified timepoint or are rescued will count as treatment failures from that timepoint. When proportion of responders (e.g., meeting HbA1c criteria; composite endpoints) is needed, the estimates, confidence intervals, and tests will be obtained using this methodology with adjustment for baseline variable (e.g., adjustment for baseline HbA1c) and stratification factor. For each treatment group, the probability of response is first modeled using a logistic regression model with baseline (e.g., baseline HbA1c) and stratification factor as the covariates. Treatment group estimates of response rate are then obtained by integrating each group's modeled probability of response over the observed distribution of baseline covariate (combined across groups). For analysis of proportion of subjects achieving therapeutic glyceemic response (HbA1c < 7%), the difference in response rate between the saxa-dapa arm and the insulin arm will be displayed along with standard error and 95% confidence intervals using the methodology of Zhang, Tsiatis and Davidian and Tsiatis, Davidian, Zhang and Lu. Non-Inferiority will be demonstrated if the upper bound of the 95% confidence interval is less than 10%.

When there are less than 5 responders in any treatment group, the unadjusted (and difference in) proportions, exact 95% confidence interval, and p-values from the Fisher's exact test (when applicable) will be provided.

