4.3 Exploratory Endpoints

- 1) In a sub-study, change from baseline in mean amplitude of glucose excursions (MAGE) of 24 hour glucose readings measured by Continuous Glucose Monitoring (CGM) at Week 2, Week 12, and Week 24 (Phase V[®] CGM Analytics variable name MAGE_SC see appendix 1).
- 2) In a sub-study, change from baseline in the mean value of 24 hour glucose readings measured by Continuous Glucose Monitoring (CGM) at Week 12 and Week 24 (Phase V[®] CGM Analytics variable name BGMEANALL see appendix 1).
- 3) In a sub-study, change from baseline within-subject, within-day in the standard deviation of 24 hour glucose readings measured by Continuous Glucose Monitoring (CGM) at Week 2, Week 12 and Week 24 (Phase V[®] CGM Analytics variable name WPWDSDDY see appendix 1).
- 4) In a sub-study, change from baseline in the percentage of time spent in the euglycemic target range of \geq 71 mg/dL (3.9 mmol/L) and \leq 180 mg/dL (10.0 mmol/L) as measured by CGM at Week 2, Week 12, and Week 24 (Phase V[®] CGM Analytics variable name CGM_GE71_LE180_PCTTIME see appendix 1).
- 5) In a sub-study, change from baseline in the percentage of time spent with glucose \leq 70 mg/dL (3.9 mmol/L) as measured by CGM at Week 2, Week 12, and Week 24 (Phase V[®] CGM Analytics variable name CGM_HYPO_PCTTIME see appendix 1).
- 6) In a sub-study, change from baseline in the percentage of time spent with glucose \leq 70 mg/dL (3.9 mmol/L) as measured by CGM between midnight (12am) and 6am at Week 2, Week 12, and Week 24 (Phase V[®] CGM Analytics variable name CGM_NOC_HYPO_PCTTIME see appendix 1).
- 7) Change from baseline in HbA1c at Week 52.
- 8) Change from baseline in total body weight at Week 52
- 9) Proportion of subjects with confirmed hypoglycemia [defined as: blood glucose \leq 70 mg/dL (3.9 mmol/L) recorded in the hypoglycemia module of the CRF] at Week 52

- 10) Proportion of subjects achieving a therapeutic glycemic response, defined as HbA1c < 7.0%, without any hypoglycemia, at Week 52
- 11) Proportion of subjects achieving a therapeutic glycemic response, defined as HbA1c < 7.0%, at Week 52
- 12) Proportion of subjects requiring rescue or discontinuation for lack of glycemic control) at Week 24 and Week 52
- 13) Time to treatment intensification (addition of non study insulin or other anti-diabetic therapies for rescue therapy or discontinuation for lack of glycemic control) at Week 24 and Week 52

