- 14) Proportion of subjects achieving a therapeutic glycemic response, defined as HbA1c ≤ 6.5%, at Week 24 and Week 52
- 15) Proportion of subjects achieving a therapeutic glycemic response, defined as HbA1c ≤ 6.5%, without any hypoglycemia at Week 24 and Week 52
- 16) Change from baseline in average glucose values and postprandial glucose values measured by 6-point SMBG profiles at Week 12, Week 24, and Week 52
- 17) Change from baseline in patient-reported treatment satisfaction, quality of life, and barriers to medication adherence at Week 12, Week 24 and Week 52

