- In a sub-study, change from baseline in the mean value of 24-hour glucose readings measured by Continuous Glucose Monitoring (CGM) at Week 2 (testing non-inferiority, using a non-inferiority margin of 12 mg/dL)
- Proportion of subjects achieving a therapeutic glycemic response, defined as HbA1c $< 7.0\%$ at Week 24 (testing non-inferiority, using a non-inferiority margin of 10%)

Analyses of secondary and exploratory endpoints specifically designed for sub-studies (CGM) will be performed using the subsets of the Randomized Subjects data set for the sub-studies.

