7.5.5.2 Glycemic Rescue or Discontinuation from Study treatment due to Lack of Efficacy

The proportion of subjects requiring treatment intensification (glycemic rescue or discontinue study treatment for lack of efficacy) up to Week 24 / 52 will be assessed by summarizing the difference in the percentages between treatment groups and by a time-to-event analysis using the Kaplan-Meier methodology.

Time to treatment intensification will be analyzed using a Cox proportional hazards model. Estimates of hazard ratio and 95% confidence intervals will be provided. Kaplan-Meier plots^{□1} of time to intensification at Weeks 24 and 52 will be calculated and plotted by treatment group. Unless otherwise specified, the plot will be presented only when there are at least 10 events in one treatment group. Additionally, a table will accompany the plot and will display the Kaplan-Meier estimates of the cumulative proportion (with 95% CI calculated based on Greenwood's method^{□2} when applicable) of subjects with event at specific time points by treatment group. If the estimated lower bound of 95% CI is below 0 or the estimated upper bound of 95% CI is over 1, then it will be restricted to 0 or 1 respectively. For the analysis during 24 / 52 weeks, all subjects will be censored at Week 24 / 52 visit (end of ST treatment/end of LT treatment) if treatment intensification has not occurred by then. Subjects rescued at Week 24 / 52 will be counted as having an event for the analysis.

Composite response endpoints (glycemic control without hypoglycemia), will be analyzed using logistic regression with adjustment for baseline HbA1c value and/or the stratification factor. None of the exploratory endpoints will be statistically tested

In addition, an analysis of the proportion of subjects not rescued and achieving glycemic response (defined as HbA1c < 7%) in subjects from the Short-term Completers Data Set at time points during the LT period will be performed using the same methodology described above (with adjustment for end of ST HbA1c measurement). Subjects discontinued or missed measurements (regardless of the type of missing) at the specific time point will be considered as not achieving glycemic response.

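### SAP 7.1.8 carries HbA1c non-response forward in the same way as rescue, so a Week 24 non-responder is scored a failure at Week 52 whatever the Week 52 value

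*SAP*

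**What the plan says.** Section 7.1.8 sets the general method for responder proportions at any Week t ("Unless otherwise specified, the proportion of subjects" opens the section). Its failure rule is that subjects who do not show glycemic response "at a specified timepoint or are rescued will count as treatment failures from that timepoint".

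The Week 52 endpoints in Section 4.3 are stated by visit. Endpoint 11 is "Proportion of subjects achieving a therapeutic glycemic response, defined as HbA1c < 7.0%, at Week 52". Endpoint 14 is "Proportion of subjects achieving a therapeutic glycemic response, defined as HbA1c ≤ 6.5%, at Week 24 and Week 52". Endpoints 10 and 15 add absence of hypoglycemia to the same HbA1c criteria. None of the four makes Week 52 response depend on response at Week 24.

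Section 7.5.5.2 adds a responder analysis at long-term visits in the Short-term Completers Data Set. It "will be performed using the same methodology described above (with adjustment for end of ST HbA1c measurement"). It scores missing data at the visit: "Subjects discontinued or missed measurements (regardless of the type of missing) at the specific time point will be considered as not achieving glycemic response".

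Section 7.1.1.3 takes Week 24 glycemic response from the measurement assigned to Week 24. If there is none, the last earlier post-baseline value is used. For a subject rescued before Week 24, it is the last value before rescue.

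**The concern.** The words *from that timepoint* follow both triggers, and no other section confines the carry-forward to rescued subjects. A programmer who follows the sentence would score a subject with HbA1c 7.1% at Week 24 and 6.8% at Week 52 as a Week 52 failure. Endpoint 11, as defined, makes that subject a responder.

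At stake are the Week 52 response rates in the final study report. Under the literal rule, the proportion can only stay level or fall after Week 24, and any subject who first reaches the threshold later is lost. Two programmers working from this SAP could report different Week 52 rates from the same data.

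**Working it through.** **1. The plan's own figure.** The SAP gives no figure for responder rates at Week 52, so there is none to reproduce on this point.

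**2. The sections side by side.**

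| Place | Rule | Reach of a Week 24 non-response |
|---|---|---|
| 7.1.8 | Non-response or rescue leads to failure from that time point | Week 24 and Week 52 |
| 4.3, endpoints 10, 11, 14, 15 | HbA1c criterion at the named visit | Week 24 only |
| 7.5.5.2, long-term analysis | Adjusts for HbA1c at the end of the short-term period | Implies that later status is still open |
| 7.1.1.3 | Week 24 response from the Week 24 measurement | Says nothing on Week 52 |

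The first two rows conflict directly. The third is a matter of fit. If every subject at or above 7.0% at the end of the short-term period were already a fixed failure, much of what the covariate explains would be settled by definition, and adjusting for it would make little sense.

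**3. Size, first set of assumptions.** Let p24 be the Week 24 response rate, a the share of Week 24 responders still responding at Week 52, and b the share of Week 24 non-responders who meet the criterion at Week 52.

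- By visit status: p24 × a + (1 − p24) × b
- Under the literal rule: p24 × a
- Understatement: (1 − p24) × b

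Assumed ranges, not from the SAP: p24 from 0.20 to 0.40, a from 0.60 to 0.80, b from 0.05 to 0.15.

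- Smallest: (1 − 0.40) × 0.05 = 0.03
- Largest: (1 − 0.20) × 0.15 = 0.12
- Example with p24 = 0.30, a = 0.80, b = 0.10: by visit 0.24 + 0.07 = 0.31; literal rule 0.24; understatement 0.07

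This gives 3 to 12 points. The value of a does not affect the loss.

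**4. Size, second set of assumptions.** HbA1c is taken as bivariate normal at Weeks 24 and 52, with mean 7.3% and SD 1.1 at both visits and correlation 0.6 to 0.8. The 1.1 equals the SD in Section 5, but that one belongs to the sample size for the change from baseline. Using it for HbA1c level is an assumption.

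- Response by visit status: P(HbA1c < 7.0) = Φ((7.0 − 7.3)/1.1) = Φ(−0.273) = 0.393
- Response under the literal rule: P(both visits < 7.0)

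| Correlation | Literal rule | Understatement |
|---|---|---|
| 0.6 | 0.251 | 0.142 |
| 0.7 | 0.271 | 0.122 |
| 0.8 | 0.294 | 0.099 |

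This gives 10 to 14 points. Taken together, the two sets span roughly 3 to 14 points.

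**The case against.** The strongest reply is that by-visit scoring is plainly meant. Section 7.1.8 speaks of the proportion at Week t, the endpoints name their visits, and the covariate in Section 7.5.5.2 presupposes that later status can change. That is probably the intent. It does not settle the matter, because the one sentence that states the failure rule says otherwise and nothing overrides it.

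The second reply is that nothing tested is touched. This stands. Endpoints 10, 11, 14 and 15 are exploratory, and Section 7.5.5 says that no exploratory endpoint is tested. No error rate or ranked claim changes.

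Three stronger readings are tempting and are not supported:

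- **Earlier visits count too.** A reader might infer that HbA1c above 7.0% at Week 4, 8, 12 or 18 already makes a subject a Week 24 failure. That would shrink both arms in the ranked responder endpoints and make the margin for the last one ("at Week 24 (testing non-inferiority, using a non-inferiority margin of 10"%) easier to meet. Section 7.1.1.3 bases Week 24 response on the Week 24 measurement, and no responder endpoint in Section 4 names those earlier visits. Section 8.4 only assigns HbA1c values to visit windows. The margin argument could not reach the composite of response without hypoglycemia in any case, since that is a superiority test.
- **Section 7.5.5.2 expressly scores observed non-response by visit.** It does not. Its sentence covers discontinued subjects and missed measurements, within one analysis of short-term completers. It sets no rule for an observed value above the threshold.
- **The rule favours one arm.** Whichever arm gains more late responders would lose more, but neither calculation yields a between-arm difference, and the SAP gives no figures from which to derive one.

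**Conclusion.** The concern holds for Week 52 only. As written, Section 7.1.8 makes Week 24 non-response final, against the by-visit HbA1c criteria of exploratory endpoints 10, 11, 14 and 15, and in poor fit with the covariate in the long-term responder analysis. The reported Week 52 response rates would be biased downward by roughly 3 to 14 percentage points. That range rests wholly on assumed response rates, HbA1c distributions and correlations that the SAP does not give, so it shows scale and is not a prediction. The ranked Week 24 secondary endpoints and their tests stand. The correction is still worth making, because the rule is stated, would distort reported rates if followed, and is easily repaired.

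**What to change.** Replace the failure sentence in Section 7.1.8 with wording such as:

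> Non-response is assessed separately at each time point: a subject whose HbA1c does not meet the criterion at a visit is a non-responder at that visit only. For this scoring, a rescued subject counts as a non-responder at that and every later time point.

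Keep missing values out of this sentence. A general rule that missing means failure would collide with the last-observation rule for Week 24 response in Section 7.1.1.3.

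Separately, reconcile how missing and rescued subjects are scored across three places: Section 7.1.1.3 (last earlier value, or last value before rescue), Section 7.1.8 (rescue is failure) and Section 7.5.5.2 (missing is non-response, in the completer analysis).

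The cost is one replaced sentence plus a short cross-check of those sections. No sample size, margin or test changes.

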7.5 Efficacy

7.5.1 Overall Efficacy Summary

Efficacy analyses will be performed using the randomized subjects data set. For the non-inferiority endpoints, the analysis will also be performed in the evaluable subject data set. All analyses included in the hierarchical testing below, including the primary analysis, will use the randomized

subject data set. The analyses using the evaluable subject data set will not be included in the hierarchical testing.

All the main analyses will be conducted using values prior to rescue/intensification of treatment or treatment discontinuation. Values collected after this time will be excluded from analyses. Sensitivity analysis using data regardless of rescue or treatment discontinuation will also be performed for the primary efficacy endpoint to assess the robustness of the primary efficacy results.

The primary endpoint is the change in HbA1 from baseline at Week 24 visit. The primary endpoint will be tested for non-inferiority for saxagliptin plus dapagliflozin versus insulin at the $\alpha = 0.025$ level (one sided), within a non-inferiority margin of 0.30%. If non-inferiority is demonstrated for the primary endpoint, the statistical tests for the secondary efficacy endpoints will be performed. The secondary endpoints then will be tested sequentially in the order that they appear below and in the objectives section of the protocol. Each comparison will be tested at the $\alpha = 0.05$ (two-sided) level. Statistical tests between the dapagliflozin plus saxagliptin group and insulin group will be only performed for a given secondary endpoint if all previous sequential tests are statistically significant. Otherwise, the testing procedure will stop at the secondary endpoint that does not reach statistical significance. These secondary endpoints are all testing superiority, with the exception of the fourth and fifth bullets below which are testing non-inferiority.

- Change from baseline in total body weight at Week 24 (tested for superiority)
- Proportion of subjects with confirmed hypoglycemia [defined as: blood glucose ≤ 70 mg/dL (3.9 mmol/L) recorded in the hypoglycemia module of the CRF] at Week 24 (testing superiority)
- Proportion of subjects achieving a therapeutic glycemic response, defined as HbA1c $< 7.0\%$, without any reported hypoglycemia (for the duration of the Short-term Period) at Week 24 (testing superiority)

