7.5.2 Primary Efficacy Analysis

The primary endpoint is the change in HbA1 from baseline at Week 24 visit. The primary endpoint will be tested for non-inferiority for saxagliptin plus dapagliflozin versus insulin at the $\alpha = 0.025$ level (one sided). The primary analysis of the change in HbA1c from baseline at Week 24 visit will be based on a longitudinal repeated measures analysis using 'direct likelihood'. The model will use subjects in the primary efficacy data set (i.e., randomized subjects data set) who have a baseline assessment and at least one post-baseline open-label

treatment period assessment. The SAS procedure PROC MIXED will be used. The preferred model will include the fixed categorical effects of treatment, week, randomization stratification factor (background medication of metformin alone vs. metformin + SU) and treatment-by-week interaction as well as the continuous fixed covariates of baseline measurement and baseline measurement-by-week interaction (see Model 7.1.2.1 in Section 7.1.2). An unstructured matrix for the within-subject error variance-covariance will be used. The denominator degrees of freedom will be calculated according to the Kenward-Roger method. A number of back-up models are defined in the Core statistical analysis plan (Section 7.1.2) in case of non-convergence of the preferred model or other issues. Data collected outside the analysis window (defined in Section 8 of this SAP) after subjects discontinued study medication will also be excluded from the primary analysis. Point estimates and 95% confidence intervals for the mean change within each treatment group as well as the difference in mean change between the saxagliptin plus dapagliflozin versus insulin will be calculated. If the upper limit of the 95% confidence interval of the difference is $< 0.3\%$, then saxagliptin plus dapagliflozin as add-on therapy to metformin with or without SU will be considered non-inferior to insulin as add-on therapy to metformin with or without SU.

Sensitivity Analyses

The following sensitivity analyses will be carried out for the primary end point:

- Primary analysis will be repeated using Evaluable Subjects data set.
- Primary analysis will be repeated using all available values regardless of rescue or treatment discontinuation
- An ANCOVA analysis using values prior to rescue or treatment discontinuation (LOCF will be used if the week 24 value is not available)

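### The non-inferiority rule for the proportion with HbA1c < 7% tests the wrong confidence bound: a clearly worse response rate would pass and a clearly better one would fail

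*SAP*

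**What the plan says.** Section 7.1.8 gives the method for the HbA1c < 7% responder endpoint: "the difference in response rate between the saxa-dapa arm and the insulin arm will be displayed along with standard error and 95% confidence intervals". The decision rule follows: "Non-Inferiority will be demonstrated if the upper bound of the 95% confidence interval is less than 10" percent.

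Section 7.5.1 places this endpoint fifth and last in the hierarchical sequence, described as "at Week 24 (testing non-inferiority, using a non-inferiority margin of 10" percent. Table 7.5.4-1 repeats the 10%. Neither place gives the margin a sign, names a confidence bound or defines the contrast. Section 7.5.4 names the estimation method but adds no rule.

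For the primary endpoint, Section 7.5.2 says that "the difference in mean change between the saxagliptin plus dapagliflozin versus insulin will be calculated" with a 95% confidence interval, and non-inferiority holds if the upper limit is below 0.3%.

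**The concern.** Reaching HbA1c < 7% is the favourable outcome, whereas a rise in HbA1c is unfavourable. An upper-bound rule is therefore correct for the primary endpoint and wrong for the responder proportion when both differences are taken as saxagliptin-dapagliflozin minus insulin. The same form of rule has been applied to two endpoints that run in opposite directions.

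This is the only operative decision rule for a confirmatory, multiplicity-controlled test, and Section 7.5.4 ties claims to the outcome of that sequence. Followed literally, it can support a non-inferiority claim when the data show the combination to be worse, and withhold the claim when they show it to be better.

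**Working it through.** **Direction of the contrast.** The SAP does not write the subtraction as a formula, so it has to be inferred:

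- Section 7.1.8 names the saxagliptin-dapagliflozin arm first.
- Section 7.5.2 uses the same order for the primary contrast. Its upper limit of 0.3% makes sense only for saxagliptin-dapagliflozin minus insulin.
- Section 7.5.3.2 worsens the saxagliptin-dapagliflozin values by a positive delta until the upper bound exceeds 0.3. That happens only with experimental minus control.
- Sections 7.1.2 and 7.5.6 report subgroup results as a difference from control, and Section 7.5.3.1 names insulin glargine as control.

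So d = saxagliptin-dapagliflozin rate minus insulin rate. The correct criterion is lower bound > -10 points.

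**Inputs.** From the SAP: 284 evaluable per arm (Section 5), 10-point margin (Section 7.5.1, Table 7.5.4-1), two-sided 95% interval. Assumed: insulin response rate of 30%, varied over 20% to 40%, because the SAP states no responder rates; and an unadjusted Wald interval in place of the covariate-adjusted one.

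**The plan's own figure.** The SAP gives no sample size or power for this endpoint. For the primary endpoint, with margin 0.30, SD 1.1, one-sided 0.025 and 90% power:

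n = 2 × (1.96 + 1.2816)² × 1.1² / 0.30² = 282.5, i.e. 283 per arm (stated 284). Power at 284 is 90.1%. 284 / 0.95 = 298.9, i.e. 299 per arm and 598 in total. These figures reproduce and are not in dispute.

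**Formulas.** With p_I the insulin rate and p_S = p_I + d:

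- SE = sqrt{[p_I(1 - p_I) + p_S(1 - p_S)] / 284}
- Written rule: P(upper bound < +0.10) = Φ((0.10 - d)/SE - 1.96)
- Correct rule: P(lower bound > -0.10) = Φ((0.10 + d)/SE - 1.96)

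**Worked case, d = -0.10, p_I = 0.30.** SE = sqrt[(0.21 + 0.16)/284] = 0.0361. Written rule: Φ(0.20/0.0361 - 1.96) = 0.9998. Correct rule: Φ(0 - 1.96) = 0.025.

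**Probability of declaring non-inferiority, insulin rate 30% (in brackets: 20% / 40%)**

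| True d (points) | Written rule | Correct rule |
|---|---|---|
| -15 | >99.9% | 0.03% (0.01 / 0.06) |
| -10 (the margin) | 99.98% (100 / 99.9) | 2.5% |
| -5 | 98% (99.7 / 96) | 27% (35 / 23) |
| 0 | 74% (85 / 68) | 74% (85 / 68) |
| +5 | 25% (30 / 23) | 97% (99 / 95) |
| +10 | 2.5% | 99.9% (99.98 / 99.8) |
| +15 | 0.07% (0.05 / 0.08) | about 100% |

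Results with 299 per arm are nearly the same.

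**Two example outcomes, 284 per arm**

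- Observed 15% on saxagliptin-dapagliflozin against 30% on insulin: 95% interval -21.8 to -8.2 points. The whole interval favours insulin, and the written rule declares non-inferiority.
- Observed 45% against 30%: 95% interval +7.1 to +22.9 points. The whole interval favours saxagliptin-dapagliflozin, and the written rule fails it.

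**The case against.** The strongest reply is that a difference between two arms does not fix a subtraction. If the programmers take insulin minus saxagliptin-dapagliflozin, an upper bound below 10% is the right criterion. The primary contrast is not written as a formula either; its direction is read from the rule making sense, and the same charity here would give the reversed contrast. This stands as far as the missing formula goes. It does not rescue the rule: no section signals a reversed contrast for this one endpoint, and the tipping-point and subgroup sections point to experimental minus control. Even on the charitable reading, a one-sided bound on an undefined contrast does not determine a decision.

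Second, the probabilities treat the test as always reached. It is reached only after the primary endpoint and four earlier secondaries succeed, including superiority on HbA1c < 7% without hypoglycemia. A combination 20 points worse on HbA1c < 7% would seldom get that far. This also stands: the figures describe the test taken alone, not the trial-wide chance of a false claim. The same gatekeeping makes the opposite error the more practical one, since a combination that passes the earlier tests may well have the higher response rate and would then be failed.

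Third, the objective is clear and the interval will be displayed, so a misdirected conclusion would be noticed. That is likely, but correcting the rule after the results are seen would be a post hoc change to a confirmatory criterion in an open-label trial.

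**Conclusion.** The concern holds. On the natural reading of the contrast, the rule tests the wrong side, and the unsigned 10% elsewhere in the SAP does not correct it. At the non-inferiority margin the test passes almost always (99.9% to 100% over insulin rates of 20% to 40%) instead of 2.5% of the time. At a true advantage of 10 points it passes 2.5% of the time instead of 99.8% or more. At zero difference the two rules perform identically.

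The sizes rest on 284 per arm, the assumed insulin rates and an unadjusted Wald interval, and they apply to this test alone, given that it is reached. The error of direction depends on none of those assumptions. It touches only the last-ranked secondary endpoint: the primary analysis, the sample size and the four earlier secondary tests are unaffected. It must still be corrected, because a confirmatory claim depends on it.

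**What to change.** Replace the decision sentence in Section 7.1.8 with wording to this effect: *Non-inferiority will be demonstrated if the lower bound of the two-sided 95% confidence interval for the difference in response rate (saxagliptin plus dapagliflozin minus insulin glargine) is greater than -10 percentage points.* State the direction of subtraction and the signed margin in Table 7.5.4-1 as well.

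Defining the contrast as insulin minus saxagliptin-dapagliflozin and keeping the upper bound would be arithmetically equivalent, but it would reverse the orientation used for the primary endpoint, so the first form is preferable.

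The cost is one sentence and one table entry, made before the short-term database lock. No new data, analysis method or sample size is needed.
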